**Evaluation of Dental Anxiety in Patients Undergoing Second Stage Surgery with Er,Cr:YSGG Laser
Treatment: Randomized Clinical Trial**

Approval Date: 24/11/2017

Study protocol

This study was carried out on 96-healthy individuals, aged between 20-75 years, who underwent dental implant therapy in XXX University, Faculty of Dentistry, Departments of Oral and Maxillofacial Surgery and Periodontology and whose healing caps will be placed after second stage implant surgery. The findings of Eroğlu et al. were used to determine the sample size. According to this, it was calculated that 36 patients each should be included in the experimental and control groups in order to determine a 50% decrease in dental anxiety levels (β : 0.8, α :0.05). Considering the possible follow-up losses, it was decided that both groups consist of 48 patients. 96 patients were divided into two groups by randomization procedure (GraphPad Prism). The study was approved by XXX University, Faculty of Medicine, Ethics Committee of Clinical Research (XXX-01-24.11.2017). Authors declare that there was a preoperative information performed to all of the patients. All surgical procedures were carried out in accordance with the Helsinki Declaration. The osseointegrated implants embedded under the oral mucosa were exposed with a scalpel (Group 1) or Er,Cr:YSGG laser (Group 2). Totally-304 osseointegrated implants in 96 patients were evaluated clinically and radiographically in detail before the second stage surgical procedures. Patients without sufficient-keratinized gingiva at the implant shoulder region, those the tissue transposition techniques should be applied, those with high DAS score, implants that can not be localized due to gingiva thickness, implants with the possibility of bone overlap on closure screw and scalpel incisions greater than 1cm length (per implant) were excluded. For these reasons, 10 patients in Group 1 and 4 patients in Group 2 were excluded from the study. After all these evaluations, the second stage implant surgery was initiated with scalpel for 172 osseointegrated implants in 38 patients. The second stage implant surgery of 106 osseointegrated implants (Implant Direct, CA, USA) in 44 patients was performed with Er,Cr:YSGG (Figure 1).

All surgical procedures were performed by the same surgeon in both groups. In the scalpel group, second stage surgical procedures were carried out with standard technique. Local anesthesia was performed with 2ml of 40mg/ml articaine+ 0,012 mg/ml epinephrine (Maxicaine Fort, Vem İlaç San. ve Tic. Ltd. Şti, İstanbul, Türkiye) preoperatively. Incision was made on the area where the closure screw was reflected from the overlying mucosa and the closure screw was exposed. After insertion of the appropriate healing abutment, the procedure was completed by suturing if necessary. In the laser group, Er,Cr:YSGG laser (WaterLase iPlus; USA Biolase Technology Inc., Irvine, CA) with wavelength of 2780 nm was used on "implant recovery" setting suggested by the manufacturer and according to the recommended guidelines (pulse duration of 140–200 μ s, repetition frequency of 100 Hz, H mode, output power of 2.75 W, and air/water proportion of 10/10%). MZ5 application tip was used in non-contact mode with target tissue to expose the closure screw and the appropriate healing abutment was placed.

Before the operation, all patients were informed about the method by which the implants would be exposed and informed consent was obtained from all participants. The patients were taken to the waiting room on the day of the second stage implant surgery and were asked to fill the STAI and DAS questionnaires for evaluating their anxiety levels. The STAI questionnaire was repeated in the control session (Post-op STAI) one week after the operation in order to verify whether the anxiety levels depend on the patient's general anxiety or due to the surgical procedure. In addition, demographic information such as age and gender, daily analgesic use after the operation and VAS scores during the operation and on the 1st, 2nd and 3rd days after the operation were recorded. Patients were

divided into four groups according to analgesic use. Surgical procedures and patient evaluations (preoperative and postoperative) were performed by different physicians due to single-blind study design.

Evaluation of Anxiety

STAI questionnaire, consisting of two parts with twenty questions each, was used to evaluate the level of state and trait anxiety in the participants (STAI-S: STAI State questionnaire and STAI-T: STAI Trait questionnaire). Both parts were evaluated separately. Patients' answers to each question were scored between 1-4 points. A total of 20-37 anxiety scores were assessed as minimum level of anxiety or none, 38-44 points as moderate and 45-80 as high.

In order to evaluate dental anxiety before treatment, DAS questionnaire consisting of 4 items including multiple choice answers was used. Patients' answers to questions were scored between 1-4 points. The total score of the questions in the questionnaire ranged from 4 to 20, and 4-11 points were interpreted as low level dental anxiety, 12-14 points as moderate and more than 14 points as high.

Statistical Analysis

In the evaluation of the demographic data Chi-squared test was used for the categorical variables to analyse the frequencies and ratios. For continuous variables, Student's t-test was used when normal distribution was provided and Mann-Whitney U test was used when normal distribution was not provided. In the evaluation of DAS findings, anxiety levels in each group were examined by Chi-squared test. However, Mann-Whitney U test was used to determine the differences between the groups. VAS findings were analyzed by considering the generalized linear mixed model (GLMM) method based on Poisson distribution and AR (1) variance covariance matrix. Correlated p values obtained from the Holm-Tukey multiple comparison method were used for the comparisons of the least squares means in GLMM. In the GLMM model, the effects of the variables (group, time and analgesic consumption) on VAS values and their interactions were modeled. In the analysis of the findings of the STAI-S and STAI-T scales, the cross tabulations of the groups and anxiety categories were examined by the Chi-squared test. Mann-Whitney U test was used for comparisons between groups, and Wilcoxon test was used for intergroup comparisons. p values < 0.05 and 0.01 were accepted as statistically significant. All statistical analyzes used in the study were performed on the SAS 9.4 software. In the determination of the power of the statistical tests, the SAS software was used for VAS variables, and the G*Power software was used for the STAI S and T variables.

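### Patients with a high DAS score are removed from the allocated groups although DAS is itself compared between groups: the comparison is truncated, may be biased, and covers only low or moderate dental anxiety

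*Combined protocol and SAP*

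**What the plan says.** The Study protocol section describes 96 patients randomised to two groups of 48. It then lists reasons for exclusion, among them "those with high DAS score, implants that can not be localized due to gingiva thickness". No cut-off is given there. The exclusions are reported by group, with all reasons pooled: 10 in the scalpel group and 4 in the laser group.

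The Evaluation of Anxiety section sets the DAS bands: "4-11 points were interpreted as low level dental anxiety, 12-14 points as moderate and more than 14 points as high". It describes DAS as a measure taken before treatment ("In order to evaluate dental anxiety before treatment, DAS questionnaire consisting of 4 items"). On timing, the Study protocol says that on the day of surgery patients in the waiting room "were asked to fill the STAI and DAS questionnaires for evaluating their anxiety levels". The same paragraph says that all patients were told before the operation how their implants would be exposed. STAI is repeated a week later; no second DAS is described.

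The Statistical Analysis section uses DAS in two ways: "In the evaluation of DAS findings, anxiety levels in each group were examined by Chi-squared test", followed by "However, Mann-Whitney U test was used to determine the differences between the groups".

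The documents give no reason for the DAS exclusion, do not adapt the DAS analysis to it, and do not limit the conclusions to patients below the cut-off.

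**The concern.** The trial is named for dental anxiety, and DAS is its dental-anxiety scale. Removing patients because of a high DAS and then comparing DAS between the arms selects on the variable being compared.

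Two things are at stake.

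- **Scope.** No patient in the high band can appear in the analysis, so the trial is silent about highly anxious patients. A conclusion worded for everyone undergoing second stage surgery would claim more than was studied.
- **Validity.** The exclusions were taken out of groups already formed by randomisation. If the DAS used for exclusion is the day-of-surgery one, patients may already have known whether they would have scalpel or laser. If that knowledge raises DAS in one arm, more patients in that arm cross the threshold and are removed. The rule then discards some of the very difference that the comparison is meant to detect.

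**Working it through.** **1. The plan's own counts.** Scalpel: 48 − 10 = 38. Laser: 48 − 4 = 44. Both match the numbers operated on in the Study protocol, so the exclusions do come out of the allocated 48 + 48.

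**2. Whether numbers are the problem.** The plan needs 36 per group and allocates 48, an allowance of 25%: 36 / (1 − 0.25) = 48. Both 38 and 44 exceed 36. The issue is which patients are missing, not how many remain.

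**3. What the rule removes.** Exclusion: high DAS. Bands: 4–11 low, 12–14 moderate, above 14 high. If the word high has the same meaning in both places, the analysed patients lie in 4–14 and one of the three bands is empty in both groups by rule.

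**4. How wide the removed band is.** The section says "Patients' answers to questions were scored between 1-4 points. The total score of the questions in the questionnaire ranged from 4 to 20". Four items scored 1–4 give a maximum of 4 × 4 = 16. A maximum of 20 needs 20 / 4 = 5 points per item. The removed scores are therefore 15–16 under the stated item scoring, or 15–20 under the stated total range. The high band is emptied either way, but its width is unclear until the two statements are reconciled.

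**5. How many patients could be affected.** Reasons are not broken down, so only bounds are available:

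| | Allocated | Excluded, all reasons | Possible high-DAS exclusions |
|---|---|---|---|
| Scalpel | 48 | 10 (20.8%) | 0 to 10 |
| Laser | 48 | 4 (8.3%) | 0 to 4 |
| Total | 96 | 14 (14.6%) | 0 to 14 |

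**6. How large a difference the rule could hide.** Take the rule as fully applied, so that no retained patient is in the high band. The scalpel-minus-laser difference in the proportion with high DAS among all randomised patients then lies between two extremes:

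- 10/48 − 0/48 = +20.8 percentage points;
- 0/48 − 4/48 = −8.3 percentage points.

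After exclusion the observed difference is 0/38 − 0/44 = 0, wherever in that range the truth lies. These are limits, not estimates.

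**7. Whether the split by arm shows selection on DAS.** For 10/48 against 4/48 the odds ratio is (10 × 44) / (38 × 4) = 2.89, Fisher's exact p = 0.15. This covers all reasons together, so it neither shows nor rules out selection on DAS.

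**The case against.** The strongest reply is that restricting eligibility is a legitimate design choice, is stated openly, and narrows generalisability without itself biasing a randomised comparison. That would hold if the criterion had been applied before allocation, or on a DAS taken before patients knew their method. The documents describe neither: exclusions are counted by arm, and the only DAS described is on the day of surgery.

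Several parts of the opposing case do stand.

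- The cut-off of more than 14 is inferred from the shared word high. An earlier, undescribed DAS could have been used for screening, in which case the high band in the analysis might not be entirely empty.
- The order of telling patients the method and completing the questionnaire is not stated beyond both preceding surgery, so bias is possible, not demonstrated.
- The number excluded for DAS could be zero.

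A reader might also infer more than the text supports.

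- **That 10 against 4 shows more anxious patients removed from the scalpel arm.** Six reasons are pooled, and one of them, incision length, concerns scalpel incisions and may account for part of the imbalance.
- **That the exclusion makes the planned effect unattainable.** The target, "in order to determine a 50% decrease in dental anxiety levels", names neither a scale nor a high-anxiety rate. DAS is taken once, so no individual score is required to fall.
- **That a group-by-three-level DAS table loses a column.** Cross-tabulation of groups by category is stated for STAI-S and STAI-T; for DAS the between-group test named is Mann-Whitney.
- **That retaining patients with high STAI is inconsistent.** STAI measures state and trait anxiety, and excluding on a dental scale does not oblige the trial to exclude on that one.
- **That the share of scale values removed measures the share of patients lost.** It does not, and the scale maximum is itself contradictory.

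**Conclusion.** The concern holds in a limited form and should be dealt with. On the plan's own definitions, patients with high DAS are removed from the randomised groups, DAS is then compared between those groups, and the results apply only to low or moderate dental anxiety. Because exclusion follows allocation and may follow disclosure of the method, the between-group DAS comparison may also be biased. Neither the direction nor the amount can be established from the documents.

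The size is bounded, not known: 0 to 14 of 96 patients, at most 10/48 scalpel and 4/48 laser. This rests on two assumptions: that high means more than 14 in both places, and that the day-of-surgery DAS is the one used for exclusion. If the second fails, the risk that knowledge of the method drove exclusion falls away, but the limit on scope remains as long as the screening DAS used the same cut-off.

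**What to change.** **Preferred.** Include all randomised patients with a completed questionnaire, high DAS included, in the DAS and pre-operative STAI comparisons, in the group to which they were allocated and whatever treatment they then received. Report by arm how many patients were excluded for high DAS, how many for each other reason, and how many had no questionnaire. State which DAS was used for exclusion and whether it came before or after patients were told the method. This changes only the analysis and reporting of data already collected and leaves clinical management as it was.

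**If those data are unavailable or the criterion is kept.** State the numerical cut-off, analyse DAS level as low against moderate, and limit the title and conclusion to patients with low or moderate DAS. DAS exclusions by arm should still be reported, because narrowing the claim does not remove the possible bias.

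**In either case.** Reconcile the 1–4 item scoring with the stated total range of 4 to 20, and confirm that the bands were applied to the scoring actually used.

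**Cost.** The preferred route needs the questionnaires of up to 14 excluded patients and a rerun of the pre-operative comparisons. Pre-operative and post-operative analyses may then have different denominators (up to 48 per group against 38 and 44), which should be stated in the tables. The fallback costs wording and a narrower claim.

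### Ten scalpel and four laser patients are excluded after randomisation and no analysis of all 96 is described, so 38 v 44 is not the comparison as randomised

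*Combined protocol and SAP*

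**What the plan says.** The Study protocol section of the combined protocol and SAP fixes the group size: "Considering the possible follow-up losses, it was decided that both groups consist of 48 patients". It allocates the 96 patients at random to scalpel (Group 1) or laser (Group 2) using GraphPad Prism. It then describes a pre-surgical assessment: "Totally-304 osseointegrated implants in 96 patients were evaluated clinically and radiographically in detail before the second stage surgical procedures".

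Six exclusion criteria follow. Most are anatomical or technical, but the list includes "those with high DAS score, implants that can not be localized due to gingiva thickness" and ends with "scalpel incisions greater than 1cm length (per implant) were excluded". The result is given by allocated group: "For these reasons, 10 patients in Group 1 and 4 patients in Group 2 were excluded from the study". Surgery then goes ahead in those who remain: "After all these evaluations, the second stage implant surgery was initiated with scalpel for 172 osseointegrated implants in 38 patients", and 106 implants in 44 patients by laser.

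The same section says that patients were told their exposure method before the operation, and that STAI and DAS were completed in the waiting room on the day of surgery. It says that different physicians did the surgery and the evaluations, but not that the evaluators were unaware of allocation.

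The Evaluation of Anxiety section defines high DAS as a score above 14. The Statistical Analysis section compares DAS between groups by Mann-Whitney U and uses Chi-squared to examine anxiety levels in each group. It defines no analysis set and does not say how the 14 excluded patients are handled.

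**The concern.** Randomisation protects a comparison of the groups as allocated. Once patients are removed after allocation, that protection holds only if removal is unrelated to arm and outcome. Three features make this uncertain here.

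- **Unequal removal.** The scalpel group lost two and a half times as many patients as the laser group (10 v 4).
- **Selection on an analysed variable.** High DAS is a reason for removal, and DAS is compared between groups. The only DAS completion described is on the day of surgery. The text does not say whether the score used for exclusion was that one, or whether it came before or after the patient learned the method.
- **A criterion worded for the scalpel.** If the incision criterion means an incision actually made, it can remove only Group 1 patients. If it means an anticipated incision, it could be judged in both arms.

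At stake is whether the anxiety, pain and analgesic results can be read as randomised comparisons, and to which patients they apply.

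**Working it through.** **Inputs**, all from the Study protocol section: 48 per group; 10 and 4 excluded; 304 implants in 96 patients; 172 implants in 38 scalpel patients; 106 implants in 44 laser patients.

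**1. The plan's own counts.** 48 - 10 = 38 and 48 - 4 = 44, total 82. They close exactly. They also confirm a 48:48 allocation (38 + 10 and 44 + 4), so the 14 already belonged to allocated groups.

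**2. Imbalance in exclusions.** 10/48 = 20.8% and 4/48 = 8.3%; overall 14/96 = 14.6%. The difference is 12.5 points, with Newcombe 95% CI -1.9 to 26.8. Fisher's exact two-sided p = 0.146.

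**3. Implants.** 304 - 172 - 106 = 26 implants are outside the two retained counts. Let x be the number of these in Group 1. With at least one implant per excluded patient, x is at least 10 and at most 26 - 4 = 22.

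- Scalpel mean as randomised, (172 + x)/48: 182/48 = 3.79 at x = 10 and 194/48 = 4.04 at x = 22.
- Scalpel mean as retained: 172/38 = 4.53.
- Laser mean as randomised, (132 - x)/48: 122/48 = 2.54 at x = 10 and 110/48 = 2.29 at x = 22.
- Laser mean as retained: 106/44 = 2.41.
- Between-arm gap as retained: 4.53 - 2.41 = 2.12.
- Gap as randomised, (40 + 2x)/48: 60/48 = 1.25 at x = 10 and 84/48 = 1.75 at x = 22.
- Share of the gap already present at randomisation: 1.25/2.12 = 59% to 1.75/2.12 = 83%.

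Without the one-implant assumption, x runs from 0 to 26. The randomised gap is then 0.83 to 1.92, still below 2.12. The scalpel mean as randomised is at most 198/48 = 4.13, still below 4.53. The arithmetic needs only that the 26 implants are not among the 172 and 106. It does not depend on whether any of them had been opened.

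**4. The incision criterion.** Two readings have to be set against the described timing.

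- *Actual incision:* it arises only in Group 1, but it is known only once surgery has begun, so that removal is not pre-surgical.
- *Anticipated incision:* it fits the pre-surgical assessment, but could be judged for patients in either arm.

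The text does not settle which is meant. The criterion cannot be called both arm-specific and pre-surgical.

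**5. The DAS criterion.** Suppose that the excluding score is the analysed one, that high means above 14, and that someone was removed for it. With one cut-off for both arms and no true difference, both score distributions are cut in the same way and no difference is created. If one arm truly has higher scores, it loses more of its upper tail and the difference shrinks. The high category is then empty in the Chi-squared tables, but the Mann-Whitney comparison of scores can still be made.

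**The case against.** The best defence is that these are eligibility decisions, most of them anatomical or technical and applicable to either arm, taken at an assessment placed before surgery. The imbalance is compatible with chance (p = 0.15, interval including zero). Figure 1, which is not shown in the text available, may give the reasons by arm. Either contested criterion may have removed nobody. Both remaining groups exceed the 36 in "it was calculated that 36 patients each should be included in the experimental and control groups", so there is no shortfall against the stated sample size. Most of the implant gap was present before any exclusion if each excluded patient had at least one implant.

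All of this stands, and it limits the point. It does not remove it. A non-significant imbalance does not turn a selected subset into the randomised groups. The text does not say that those applying the criteria were unaware of allocation, and a list of reasons would not supply an analysis of all randomised patients.

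A reader might go further and infer that a scalpel-only rule selectively removed Group 1 patients, or that removing anxious patients produced a false DAS difference. The documents support neither. The incision criterion may be an anticipated length applied to both arms, no counts by reason are readable, and a common DAS cut-off can weaken a real difference but cannot create one.

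**Conclusion.** The point holds as a gap in the analysis set and in reporting. It should be fixed, but material bias is not demonstrated. After 48:48 randomisation, 20.8% of scalpel and 8.3% of laser patients are excluded, and the comparison described is 38 v 44. The Statistical Analysis section does not name the 82 as its set; that follows from the 14 being excluded from the study.

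The size and direction of any bias in the anxiety and pain outcomes are unknown. The one effect that can be bounded is that mean implants per scalpel patient rose from 3.79-4.04 to 4.53, given at least one implant per excluded patient. The exclusions widened the between-arm gap by 0.37 to 0.87 implants per patient (2.12 - 1.75 and 2.12 - 1.25). That this affects VAS or analgesic use is plausible but not shown. Because high DAS is an exclusion criterion, results from the 82 should not be extended to patients with high DAS.

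**What to change.** **DAS and pre-operative STAI.** Make the main set all randomised patients with a questionnaire, in their allocated group, and give the number available by arm. Keep the 82 as a sensitivity analysis. Do not use the DAS or incision criterion to remove randomised patients from analysis.

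**Reporting.** Tabulate exclusions by reason and arm, unless Figure 1 already does so. State when the excluding DAS score was taken relative to disclosure of the method. State when the incision criterion was assessed, and whether it meant an actual or an anticipated incision. Give implants per patient by arm for the 96 and the 82.

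**VAS, analgesic use and one-week STAI.** The 14 probably have no data. State that the groups analysed are not the groups as randomised, limit conclusions to patients without high DAS, and add missing-data sensitivity analyses. If none of the 14 has data, these cover 14.6% missing overall, 20.8% v 8.3% by arm.

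**Cost.** Analysis-set wording, one table, a re-run of the DAS and pre-operative STAI tests, and the sensitivity analyses. The main limit is that questionnaires were completed on the day of surgery, so some of the 14 may have none and restoration may be partial. For the later outcomes the change is mostly disclosure.

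### The VAS model has no term for implants per patient, although operated scalpel patients had 4.53 each and laser patients 2.41, so its group effect may mix instrument with extent of surgery

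*Combined protocol and SAP*

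**What the plan says.** In the Study protocol section, 96 patients are randomised, 48 to each arm. Before surgery, "Totally-304 osseointegrated implants in 96 patients were evaluated clinically and radiographically in detail before the second stage surgical procedures". Then "10 patients in Group 1 and 4 patients in Group 2 were excluded from the study". For those who remained, "the second stage implant surgery was initiated with scalpel for 172 osseointegrated implants in 38 patients", and "The second stage implant surgery of 106 osseointegrated implants (Implant Direct, CA, USA) in 44 patients was performed with Er,Cr:YSGG". The section does not express these counts per patient, does not comment on the difference, and describes no stratification by implant number.

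The same section has VAS recorded during the operation and on days 1, 2 and 3, and analgesic use recorded after the operation. Implant number is not named among the recorded variables, although the list of demographic items is open-ended.

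The Statistical Analysis section fits VAS with a Poisson mixed model with an AR(1) structure. Its effects are group, time, analgesic consumption and their interactions. Neither section gives an implant-number covariate, offset or sensitivity analysis.

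**The concern.** VAS appears to be recorded once per patient at each time; this is inferred from the outcome-recording paragraph. If so, a score reflects the whole session, and the average scalpel session involved nearly twice as many implants as the average laser session. If more implants mean more pain, the group term attributes to the scalpel some pain that belongs to the larger operation.

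Analgesic consumption cannot fill the gap. It is recorded after the operation and may itself respond to pain, so it is not a measure of how much surgery was done. For the same reason, a group comparison conditional on it is not the total effect of the instrument.

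What is at stake is whether a VAS difference can be credited to the laser rather than to fewer implants.

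**Working it through.** **Inputs**, all from the Study protocol section: 48 randomised per arm; 10 and 4 excluded; 304 implants evaluated in 96 patients; 172 implants in 38 scalpel patients; 106 in 44 laser patients.

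**The plan's own figures.** 48 - 10 = 38 and 48 - 4 = 44, as stated.

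**Implants per operated patient.**
- Scalpel: 172/38 = 4.526. Laser: 106/44 = 2.409.
- Difference 2.117; ratio 1.879.
- The text says that scalpel surgery was initiated for the 172, so operated is the safe word.

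**As randomised.** 172 + 106 = 278, and 304 - 278 = 26 implants were not operated on. Assume that each of the 14 excluded patients had at least one of them. Group 1 then holds 10 to 22 of the 26 and Group 2 holds 16 to 4. These limits hold even if some of the 26 belonged to patients who stayed in.

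| Group 1 share of the 26 | Scalpel mean | Laser mean | Difference | Ratio |
|---|---|---|---|---|
| 10 | 182/48 = 3.79 | 122/48 = 2.54 | 1.25 | 1.49 |
| 22 | 194/48 = 4.04 | 110/48 = 2.29 | 1.75 | 1.76 |

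1.25/2.117 = 0.59 and 1.75/2.117 = 0.83. So 59-83% of the gap was present at allocation and 17-41% arose with the exclusions.

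**Is this unusual for chance?** The document gives no SD of implants per patient, so these values are assumed. z = difference / sqrt((SD1² + SD2²)/48).
- SD 3 in both arms: SE 0.612, z = 2.04 to 2.86, p = 0.041 to 0.004.
- SD 4 scalpel, 3 laser: SE 0.722, z = 1.73 to 2.42, p = 0.083 to 0.015.

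The answer depends on the assumed SDs.

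**What the gap could do to VAS (illustration only).** The document gives no relation between implant number and pain. With an assumed log-scale effect b per implant, the gap alone multiplies the scalpel/laser VAS ratio by exp(2.117b): 1.04, 1.11, 1.24 and 1.53 for b = 0.02, 0.05, 0.10 and 0.20.

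**Precision cost of adjusting (linear approximation, assumed common within-arm SD).** Variance inflation = 1 + p(1 - p) x 2.117²/SD², with p = 38/82.
- SD 3: 1.124, so SE x 1.060.
- SD 2: 1.279, so SE x 1.131.
- SD 1.5: 1.495, so SE x 1.223.

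**The case against.** The strongest reply is that randomisation already deals with this. If the part of the gap present at allocation is chance, the error rate of the randomised comparison allows for it, and adjustment becomes a choice about precision and conditional inference on which statisticians differ. Only the part that came with the exclusions arose after randomisation, and a covariate does not undo selective exclusion. Both statements stand. They do not remove the point: the analysed patients are not the full randomised set, and a reader cannot interpret a VAS difference without knowing whether it survives adjustment for a 1.88-fold difference in extent.

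Three further objections narrow the point.
- A reader might infer that the allocation was faulty. The document does not support that. With plausible but unreported SDs, p ranges from 0.004 to 0.083.
- A reader might infer that the incision-length criterion ("scalpel incisions greater than 1cm length (per implant) were excluded") could remove only scalpel patients. It does appear specific to them, but the section places the evaluations before surgery, so an anticipated length could have been judged in either arm. The text is ambiguous.
- Some exclusion criteria concern individual implants, so the number evaluated in a patient may differ from the number exposed. The covariate therefore has to be defined.

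It is also fair that VAS did not set the sample size, which was calculated "in order to determine a 50% decrease in dental anxiety levels". VAS nevertheless has the most elaborate model in the plan and its own power determination. A baseline table of implant number is not ruled out, but it would not adjust the model.

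**Conclusion.** The point holds for VAS. The imbalance among operated patients (4.53 v 2.41, ratio 1.88) follows directly from the stated counts, and the model as written leaves it unadjusted. The as-randomised ratio of 1.49-1.76 rests on the assumption of at least one non-operated implant per excluded patient.

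A reader might go further and infer that any advantage of laser on VAS is explained by fewer implants. The document does not support that. It gives no relation between implant number and pain, and the exclusions may act in another direction, so neither the size nor the net direction of bias can be calculated. Nor does the point reach the anxiety measures taken before surgery: DAS and pre-operative STAI were completed in the waiting room, before any implant was exposed.

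This should be fixed because the remedy is cheap, but it does not by itself invalidate the VAS comparison.

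**What to change.** 1. Add to the VAS model the number of implants scheduled for exposure per patient, fixed at the pre-operative evaluation after implant-level exclusions.
2. Check its interaction with time, because a single slope assumes the same effect at all four VAS times. With the log link usual for a Poisson model, that slope also means that each implant multiplies VAS by a constant.
3. Report the group comparison from four models side by side: as planned; plus implant number; without analgesic consumption; without analgesic consumption plus implant number. Keep the planned model in the report, and label the others post hoc sensitivity analyses if outcomes are already known.
4. Report implants per patient (mean, SD, range) by arm for operated and for excluded patients, and check the counts 304, 172 and 106 against source records.

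**Cost.** One parameter for the covariate, plus three if the interaction with time is kept; no new patients or visits. The SE of the group effect rises by roughly 6-22% at assumed SDs of 3 to 1.5, before any gain from explained variance. That figure is a linear approximation. It was not derived for a Poisson mixed model with interactions, where there is no single group effect. The arm totals imply that patient-level counts exist, but the document does not list them as recorded, so they may have to be taken from the surgical records. The covariate would be chosen after the imbalance was seen, which is why the planned result must stay beside it.
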